Hypothesis 2: Survival without transplantation will be greater at 24 months of age in infants treated with corticosteroids than those treated with placebo.

Aim 3: To determine whether corticosteroid treatment after portoenterostomy will improve growth of infants with biliary atresia.

Hypothesis 3: Weight and height Z-scores at 12 and 24 months of age will be greater in the infants treated with corticosteroids than those treated with placebo.

Aim 4: To determine whether corticosteroid treatment improves biochemical indicators of each of the fat-soluble vitamins after supplementation with standard doses.

Hypothesis 4a: Treatment with corticosteroids leads to improved bile drainage (hypothesis 1) which, in turn, increases the probability that an infant will achieve

vitamin sufficiency of each of the fat-soluble vitamins following supplementation of AquADEK®.

Hypothesis 4b: Treatment with corticosteroids leads to improved bile drainage (hypothesis 1) which, in turn, reduces the dose required for supplementation and the length of time of supplementation for each of the fat-soluble vitamins.

Aim 5: To determine whether corticosteroid treatment after portoenterostomy will decrease the incidence of persistent ascites or ascites that requires medical treatment.

Hypothesis 5: The incidence of ascites will be decreased at 12 and 24 months of age in infants treated with corticosteroids than those treated with placebo.

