No medical therapy has been developed to date that effectively halts or reverses cholestasis and hepatic injury in children with biliary atresia. The only therapeutic choice to increase bile flow and improve jaundice is the surgical portoenterostomy, in which the fibrotic extrahepatic bile ducts are completely excised and an intestinal conduit is anastomosed to the transected surface of the porta hepatis in a Roux-en-Y fashion. Occasionally the gall bladder is anastomosed to the porta if the distal biliary tree is still patent, the so-called gall bladder Kasai. If performed within the first 60 days of life by experienced surgeons, the portoenterostomy should yield bile drainage from the liver into the intestinal tract in 67-82% of patients^{7,42,43}, resulting in increased pigmentation of the stools and resolution of jaundice. Improvement in bile drainage decreases to 45-62% of infants when surgery is performed between 60-90 days of life, and to 10-44% if beyond 90 days of life. Therefore, prompt diagnosis and timely execution of portoenterostomy are critical to improved success of the surgical treatment.

Despite the potential for improved bile drainage, portoenterostomy does not stop the inflammatory intrahepatic injury; cholestasis and ongoing cellular injury lead to cirrhosis in most patients. In the absence of other proven therapeutic options, current clinical care is primarily supportive, and includes optimizing nutrition, promoting choleresis, and preventing/treating ascending cholangitis. Ultimately, >70% of all children with biliary atresia will require liver transplantation because of failure of the portoenterostomy or

complications of end-stage liver disease. Therefore, the development of novel effective therapies to improve post-operative bile drainage and reduce or prevent progressive hepatic fibrosis in biliary atresia is a high priority, with the potential to dramatically improve long-term outcome and reduce/delay the need for liver transplantation. One such potential therapy is high-dose corticosteroids following portoenterostomy.

2.D2. Corticosteroid Treatment

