the posttranslational carboxylation of glutamic acid to gamma-carboxyglutamyl residues in factors II (prothrombin), VII, IX, and X and proteins C and S. The major sign of vitamin K deficiency is coagulopathy. The dietary form of vitamin K is vitamin K₁ and as with the other fat soluble vitamins, vitamin K absorption requires the normal flow of bile into the intestinal lumen. Malabsorption of vitamin K in cholestasis as well as antibiotic use that impairs intestinal bacterial production (vitamin K₂), can lead to vitamin K deficiency. Vitamin K status is measured clinically by prothrombin time (PT) which is an index of vitamin K dependent clotting factors. Vitamin K deficiency is suggested when the PT is prolonged yet the partial thromboplastin time (PTT) is within normal range. A diagnosis of vitamin K malabsorption and deficiency is established when the prothrombin time normalizes after parenteral vitamin K supplementation. Subclinical vitamin K deficiency states have been identified by measuring serum undercarboxylated prothrombin (PIVKA-II). This protein is considered a sensitive functional indicator of vitamin K status⁷⁰. Since the liver synthesizes some coagulation factors, coagulopathies in cholestasis can be due to vitamin K deficiency, poor liver synthetic function, or a combination of both.

Toxic manifestations of vitamin K supplementation have not been observed⁵⁵.

4.N6. Fat-soluble Vitamin Supplementation

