Prior to unmasking the study and the start of any formal analyses, the data for each variable will be examined to identify unusual values that need to be queried, patterns of missing values and whether their distributions are non-Gaussian (i.e., have significant skewness and kurtosis). These analyses are, in general, performed conditional on one or more covariates known to affect the variable being studied; for example, values may be examined conditioned on age of the infant or age at time of portoenterostomy. Data from variables with non-Gaussian distributions will be transformed, if necessary, before building statistical models. Missing data patterns will be examined and, when necessary for the data analysis, missing data may be imputed by appropriate methods depending on the pattern and mechanism of the missing data. Baseline variables will be compared between groups. If a baseline variable is identified as significantly different between groups and it may affect the outcome measure, the analysis of the outcome measure will be repeated with this baseline variable included as a covariate. All models will include clinical site as a random effect.

Aim 1: To determine whether corticosteroid therapy decreases serum bilirubin concentration after portoenterostomy.

Hypothesis 1a: The probability of an infant having good bile drainage at 6 month after portoenterostomy (as defined by a serum total bilirubin level <1.5 ml/dL) will be greater in subjects treated with corticosteroids than in those treated with placebo.

This is the primary hypothesis of this study, upon which the sample size was calculated. A generalized linear model (e.g., a logistic regression model) with random effects will be used to test this hypothesis. The dependent variable is dichotomous: whether the infant has good bile drainage or not; transplantation or death is considered a failure in all analyses. The covariates that will be included in the model are the treatment group, baseline total bilirubin level, age of the infant at portoenterostomy, complications before the surgery, gender and race of the infant, presence of major congenital anomalies, as well as site as a random effect. The test of the primary hypothesis is a test of whether the coefficient of treatment group is zero.

Hypothesis 1b: Improved bile drainage (as defined by a serum total bilirubin level <1.5 mg/dL) will remain for a longer period in infants treated with corticosteroids than in those treated with placebo.

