Each vitamin will be analyzed separately. For hypothesis 4a, each subject will be classified as having achieved or not achieved vitamin sufficiency, first with supplementation and then without supplementation. Vitamin sufficiency will be defined as having achieved the target concentration ranges specified in Section 4.N8. Although we can model the outcome as a function of treatment group, the underlying hypothesis is that the outcome is a function of bilirubin level. Therefore, we will model the outcome by logistic regression using bilirubin as a surrogate for bile drainage; bilirubin may be included in the model either as a continuous measure or as a dichotomy where <1.5 mg/dL is defined as good bile flow and ≥ 1.5 mg/dL as inadequate bile flow. Gender and race of the infant, presence of major congenital anomalies, as well as site as a random effect will be included as covariates.

Hypothesis 4b: Treatment with corticosteroids leads to improved bile drainage (hypothesis 1) which, in turn, reduces the dose required for supplementation and the length of time of supplementation for each of the fat-soluble vitamins.

As in hypothesis 4a, each vitamin will be analyzed separately. There are two components to this hypothesis. The first is the total amount of supplementation and the second is the length of supplementation. We will compute the total amount of supplementation up to 6 months of age as the first dependent variable and the time to achieving target concentrations without supplementation as the second dependent variable. The first variable (after transformation) will be analyzed by a random effects model with bilirubin as the independent variable and the same covariates as in hypothesis 4a. The second variable will be modeled by Cox regression with the same independent variable and covariates.

Aim 5: To determine whether corticosteroid treatment after portoenterostomy will decrease the incidence of persistent ascites or ascites that requires medical treatment.

Hypothesis 5: The incidence of ascites will be decreased at 12 and 24 months of age in infants treated with corticosteroids than in those treated with placebo.

Similar to hypothesis 2, a Cox proportional hazards model will be fitted to the time to diagnosis with ascites.

Other endpoints will be analyzed similarly depending on whether they are continuous, dichotomous or time-to-event.

5.C. Data Management

5.C1. Case Report Forms

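### The Aim 4 vitamin models regress on non-randomised bilirubin but leave out age at portoenterostomy, so the bilirubin-vitamin association may be confounded

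*Protocol*

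**What the plan says.** Hypothesis 4a (protocol section 1) is a claim about a chain: "Treatment with corticosteroids leads to improved bile drainage (hypothesis 1) which, in turn, increases the probability that an infant will achieve" sufficiency of each fat-soluble vitamin. Section 5.B tests the second link of that chain: "we will model the outcome by logistic regression using bilirubin as a surrogate for bile drainage". The covariates are then fixed: "Gender and race of the infant, presence of major congenital anomalies, as well as site as a random effect will be included as covariates".

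Both parts of Hypothesis 4b inherit this set. The total amount of supplementation up to 6 months of age is modelled "with bilirubin as the independent variable and the same covariates as in hypothesis 4a". For the time to reaching target without supplementation, "The second variable will be modeled by Cox regression with the same independent variable and covariates".

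The Hypothesis 1a model in the same section has a longer list. Besides treatment, gender, race, anomalies and site it includes "baseline total bilirubin level, age of the infant at portoenterostomy, complications before the surgery". Section 5.B reuses that list for Hypotheses 1b, 2 and 3. It gives no reason for the shorter one under Aim 4.

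Section 2.D1 reports how drainage depends on age at surgery: 67-82% within the first 60 days, then "Improvement in bile drainage decreases to 45-62% of infants when surgery is performed between 60-90 days of life", and 10-44% beyond 90 days.

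**The concern.** In the models for Hypotheses 1a to 3 the tested term is randomised treatment, so leaving out a prognostic baseline variable would not confound it. In the Aim 4 models the explanatory variable is bilirubin after surgery, which nobody randomised. These are the models that depend most on adjustment for baseline confounders, and they have the shortest list.

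The general rule at the start of 5.B does not close the gap. It adds a baseline variable when that variable differs between treatment groups, not when it differs across bilirubin levels. The mention there of conditioning on age at portoenterostomy concerns data checks before unmasking.

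What is at stake is the reading of the bilirubin coefficient. If infants operated on late both drain poorly and have worse vitamin markers for some other reason, part of the association credited to drainage belongs to late surgery.

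**Working it through.** The protocol gives no sample size, effect size or power for the vitamin endpoints (section 5.A2 says there are no data for this), so there is no stated figure to reproduce.

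**Step 1. Age at surgery and drainage.** Inputs are the section 2.D1 ranges; midpoints are 74.5%, 53.5% and 27%.

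- Odds: 0.745/0.255 = 2.92; 0.535/0.465 = 1.15; 0.27/0.73 = 0.370.
- Before 60 days versus 60-90 days: 2.92/1.15 = 2.5.
- Before 60 days versus beyond 90 days: 2.92/0.370 = 7.9. The nearest and farthest range ends give 2.6 and 41.

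**Step 2. Is there a second path, from age at surgery to the vitamin outcome, outside current bile flow?** Confounding needs one.

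- *Vitamin K.* The marker is INR (4.N9), and section 4.N5 says that "coagulopathies in cholestasis can be due to vitamin K deficiency, poor liver synthetic function, or a combination of both". Section 2 says that untreated obstruction causes continuing liver injury leading to cirrhosis, so later surgery plausibly means poorer synthetic function. The protocol does not state that last step.
- *Vitamin D.* The marker is 25-OH vitamin D, which section 4.N3 says is formed in the liver. The same reasoning applies.
- *4b total dose.* Here the path is arithmetic. The count stops at 6 months of age (taken as 183 days), so the time left after surgery is 183 minus age at surgery: 123 days for surgery at day 60 and 63 days at day 120, about half.

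**Step 3. Possible size for 4a if drainage has no effect.** Assumptions: age-band shares of 60/30/10%, 50/35/15% or 40/40/20%; sufficiency of 80% in the youngest band; odds of sufficiency divided by a factor r per later band; drainage and sufficiency independent within a band. With band weights w, drainage d and sufficiency s:

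- sufficiency among good drainers = Σ w·d·s / Σ w·d
- sufficiency among poor drainers = Σ w·(1−d)·s / Σ w·(1−d)

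Worked case, shares 50/35/15% and r = 2:

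- s = 80%, 66.7%, 50%.
- Good drainers: (0.3725×0.800 + 0.1873×0.667 + 0.0405×0.500)/0.600 = 0.738.
- Poor drainers: (0.1275×0.800 + 0.1628×0.667 + 0.1095×0.500)/0.400 = 0.664.
- Crude odds ratio: (0.738/0.262)/(0.664/0.336) = 1.43, where the true value is 1.

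| r per age band | Crude odds ratio over the three mixes |
|---|---|
| 1 (age acts only through drainage) | 1.00 |
| 1.5 | 1.21-1.24 |
| 2 | 1.38-1.44 |
| 3 | 1.62-1.73 |

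Mixes with more late surgery (up to 35% beyond 90 days) and 50% sufficiency in the youngest band raise the top of the range to about 1.9. With a true drainage odds ratio of 2.0 and no direct age effect, leaving age out gives 2.00, so there is no bias.

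**Step 4. Direction for the 4b total dose.** Assume equal daily dosing from surgery and surgery at 45, 75 or 105 days, which leaves 138, 108 and 78 days. With the 50/35/15% mix and midpoint drainage, the geometric mean window is 106.8 days in poor drainers and 123.0 days in good drainers, a ratio of 0.87 where the true dose ratio is 1. Over the mixes 50/35/15%, equal thirds and 30/35/35%, and the low, middle and high drainage figures, the ratio is 0.80 to 0.88. Hypothesis 4b expects poor drainers to need more, so this bias works against it.

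**The case against.** The strongest reply is that the section 2.D1 figures establish only that age at surgery affects drainage. Sections 4.N, 4.N1 and 4.N4 explain deficiency by lack of bile acids in the gut. If that is the whole mechanism, age acts through drainage alone and leaving it out does no harm. Vitamin outcomes are also measured at 12 and 24 months of age (4.E), after repeated checks and dose adjustment toward target (4.N9, 4.N10), so depletion from the weeks before surgery should largely have been corrected. Poor synthetic function may itself partly follow from poor drainage. This stands to the extent that a reader might infer that the 4a association *is* confounded; the documents support only that it may be.

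A reader might also infer a definite inflation of the false-positive rate. With 120 infants, the step 3 assumptions give about 7% to 31% in the hypothesised direction against 2.5% nominal. That range leaves out the no-effect case (about 2.4% in simulation), uses a crude two-by-two test instead of the planned model, and takes a number of infants that the protocol does not give for these endpoints. Section 3.B reports 51% transplanted by 24 months, so about 0.49 × 140 ≈ 69 might still have a native liver; at 60 to 70 infants the same assumptions give about 5% to 19%. The figures illustrate and do not estimate. Nor does the false-positive argument carry over to the 4b total dose, where the bias has the opposite sign.

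Finally, a reader might infer that the whole Hypothesis 1a list is needed. Nothing in the documents separately supports baseline bilirubin or pre-surgical complications as confounders here, and with few insufficient infants a longer model may strain.

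What the reply does not answer is why a strong predictor of the exposure, already modelled elsewhere in 5.B, is left out of the models with a non-randomised exposure. The list is written into the protocol, so it is not a detail left to an analysis plan.

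**Conclusion.** The omission is real, and its consequence is conditional. Age at portoenterostomy strongly predicts drainage on the protocol's own figures (midpoint odds ratio about 7.9, range ends 2.6 to 41), and the Aim 4 models do not adjust for it.

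- **4a and the 4b Cox model:** the association may be confounded, most plausibly for INR and 25-OH vitamin D. The size is not in the documents. It is nil if age acts only through drainage. If drainage has no effect, the spurious 4a odds ratio is about 1.2 to 1.7 under direct age effects of 1.5- to 3-fold odds per band; the age mix, the 80% sufficiency and those effects are all assumptions.
- **4b total dose:** the second path is built into the outcome definition. Under the step 4 assumptions it gives a poor/good dose ratio of 0.80 to 0.88 where the truth is 1.0, which would hide or reverse the expected difference.

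These are secondary hypotheses without a power statement, and the primary analysis is untouched.

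**What to change.** In section 5.B, add age at portoenterostomy to the Hypothesis 4a covariate sentence. Both 4b models take their covariates from it, so no further edit is needed there. Baseline bilirubin and complications before surgery may be added if the number of events allows, but they are optional.

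The cost is about one model degree of freedom and a slight loss of precision. The variable is already used in the Hypothesis 1a to 3 models, so no new data are needed.

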3. PRELIMINARY DATA

ChiLDREN is a clinical network funded by the NIDDK with goals to: (1) establish a database of clinical information and a repository of blood and tissue samples from children with biliary atresia and other forms of neonatal liver diseases; (2) conduct clinical studies on the etiology, diagnosis and pathogenesis of infants with biliary atresia; and (3) conduct multi-center clinical trials to determine the impact of novel treatment modalities on long-term outcome of affected children. ChiLDREN is governed by a Steering Committee comprised of the principal investigators (PI) from each of the participating clinical centers and the Data Coordinating Center (DCC), and the NIDDK Program Director.

3.A. The ChiLDREN Prospective Database

ChiLDREN has developed a prospective observational database of infants with biliary atresia and other causes of cholestasis in infants. In this prospective protocol, infants with cholestasis who are ≤ 180 days old are screened and enrolled at presentation to the participating clinical sites. Clinical data collection, laboratory investigations, liver biopsy specimens, and long-term follow-up of these children will be performed in accordance with the normal standard of care for diagnosis and treatment of infants with liver disorders. In order to collect data from all clinical centers uniformly, ChiLDREN has established guidelines for gathering diagnostic, clinical and outcomes data and for collecting specimens, codified to protect subject confidentiality. The data are stored in a secure research database at the DCC and the specimens are shipped to repositories under contract to NIDDK.

Since only infants with biliary atresia can be entered into the proposed clinical trial, we describe the data and specimens collected from subjects with biliary atresia who are enrolled into the prospective database.

3.A1. Recruitment

Following diagnosis of cholestasis in an infant ≤ 180 days old, the family will be approached for recruitment into the study. Parent(s) or guardian(s) must sign written informed consent before data collection can begin.

3.A2. Baseline

Once informed consent is obtained, the coordinator will abstract information from the subject's medical chart, including the physical examination at intake. The coordinator or delegated designee will interview the parents/guardians to review the child's medical history and the relevant medical history of the immediate family.

3.A3. Surgery/Diagnosis

The timeline for follow-up is triggered by the date of the portoenterostomy for subjects with biliary atresia. The surgeon will complete a case report form that describes in detail the surgical findings. The pathologist will detail the pathological findings that are relevant to the diagnosis.

3.A4. In-patient / Discharge

Data will be collected from the time of surgery to the time of discharge.

3.A5. Follow-up

Subjects with biliary atresia will be followed closely during the first year post-portoenterostomy, at 18 and 24 months of age and then annually to 10 years of age or to the time of transplant or death, whichever comes first.

3.A6. Specimen Collection

At baseline and follow up visits, serum, plasma and urine will be collected for the repository. At the time of a liver biopsy, the portoenterostomy and transplant, specimens from the liver, gall bladder, biliary remnant and lymph node may be collected for the repository when the specimens are clinically indicated to be excised and they are not needed for diagnosis.

3.B. Current Outcome of Children with Biliary Atresia Treated at ChiLDREN Centers

One unique feature that is critical to the implementation of controlled clinical studies is the standardization of surgical and medical approaches, which will enable investigators to determine the impact of novel therapeutic interventions (such as this proposed corticosteroid clinical trial) on clinical outcomes across all participating clinical centers. In preparation for this multicenter trial, the DCC carried out a survey among the ChiLDREN clinical centers to determine the outcome of infants with biliary atresia following portoenterostomy during the periods of 1998-2001. This retrospective survey collected data on serum bilirubin levels at 6 months after portoenterostomy and the number of children requiring liver transplantation or dying from a complication of biliary atresia at or before 24 months of age. In total, portoenterostomies were performed on 118 subjects in the 4-year period. Of these, 46% had good bile flow at 6 months after portoenterostomy, and 51% underwent liver transplantation by 24 months of age.

4. RESEARCH DESIGN AND METHODS

4.A. Overview

The overall hypothesis is that therapy with corticosteroids following portoenterostomy will improve bile drainage and long-term outcome in infants with biliary atresia. This hypothesis will be tested by a multicenter prospective, randomized, double-blinded, placebo-controlled trial. Subjects will be recruited from subjects enrolled in the ChiLDREN prospective observational database study who undergo portoenterostomy for biliary atresia. The investigator or clinical research coordinator will approach the subject's parent(s) or guardian(s) and discuss the study design, benefits and possible risks with the family. After IRB-approved written consent is obtained from the parent or guardian, the clinical research coordinator will:

- Complete the Eligibility Form
- Randomize the subject to 13 weeks of treatment with placebo or corticosteroids. (The research team will be blinded to the treatment. The randomization scheme will be prepared by the DCC and implemented by the research pharmacist.)
- Collect clinical and biochemical data at 2 weeks after portoenterostomy, at 1, 2, 3, and 6 months after portoenterostomy, and at 12, 18, and 24 months of age.

All subjects will receive standard clinical care that is routinely used for all infants with biliary atresia, which will include nutritional support and medications unrelated to this trial. This routine clinical care will not be modified due to participation in this study.

4.B. Study Population

All infants enrolled in the ChiLDREN prospective database study who undergo portoenterostomy or the gall bladder Kasai operation (portocholecystostomy) for biliary atresia will be eligible for the trial. *For purposes of this protocol the term portoenterostomy will include the gall bladder Kasai procedure.* Parents/guardians will be approached about participation in this clinical trial after a decision is made by the attending physician at the ChiLDREN site that the infant will undergo an exploratory laparotomy with possible portoenterostomy, or within 72 hours after portoenterostomy. Biliary atresia is defined as a fibroinflammatory obliteration of the lumen of one or more segments of the extrahepatic biliary tree within the first 3-6 months of life. Rarely, post-operative examination of the excised biliary remnant will demonstrate that a disease process other than biliary atresia caused the biliary obstruction. If this is found in a subject already enrolled in this trial, the study drug/placebo will be discontinued and the subject will be removed from the study.

The total number of subjects to be entered in the study at all clinical sites will be 140.

4.C. Inclusion Criteria

- Portoenterostomy or gall bladder Kasai operation for biliary atresia within the previous 72 hours
- Post-conception age \geq 36 weeks
- Weight at enrolment \geq 2000 gm
- Written informed consent to participate in the study obtained prior to or within 72 hours of completion of portoenterostomy. (*Note: Families of potential subjects may be approached prior to the portoenterostomy.*)

4.D. Exclusion Criteria

- Known immunodeficiency
- Diabetes mellitus
- Presence of significant systemic hypertension for age (persistent systolic blood pressure \geq 112 mmHg)
- A serum indirect (unconjugated) bilirubin \geq 5 mg/dL for infants under 4 weeks of age or \geq 7 mg/dL for infants between 4 and 8 weeks of age
- Known sensitivity to corticosteroids
- Documented bacteremia or other tissue infection which is felt to be clinically relevant
- Known congenital infection or disease with herpes simplex virus, toxoplasmosis, or cytomegalovirus inclusion disease of the liver
- Infants whose mother is known to have human immunodeficiency virus infection
- Infants whose mother is known to be HBsAg or hepatitis C virus positive
- Infants with other severe concurrent illnesses such as neurological, cardiovascular, pulmonary, metabolic, endocrine, and renal disorders that would interfere with the conduct and results of the study
- Any other clinical condition that is a contraindication to the use of corticosteroid (e.g., bowel perforation)
- Infants who have received the live attenuated rotavirus vaccine (e.g. Rotateq) within 5 days prior to proposed administration of study drug.

In the unlikely event that the diagnosis of biliary atresia is established during exploratory laparotomy, but the surgeon did not perform a portoenterostomy (as may occur in cases of advanced cirrhosis), the subject will not be eligible for this study.

4.E. Primary and Secondary Outcome Measures

- Primary outcome measure:
Percentage of subjects with serum total bilirubin $<$ 1.5 mg/dL and with native liver at 6 months after portoenterostomy.
- Secondary outcome measures:
All measurements will be made at 12 and 24 months of age (unless noted otherwise):
 1. Serum total bilirubin concentration (and also at 3 months after portoenterostomy)
 2. Survival with native liver at 24 months of age

3. Growth
 - a. Weight for age Z-score (in subjects without ascites)
 - b. Height for age Z score
4. Serum biomarkers of sufficiency of fat-soluble vitamins
 - a. Vitamin A: molar ratio of serum retinol/retinol binding protein
 - b. Vitamin D: serum level of 25-hydroxy vitamin D
 - c. Vitamin E: ratio of serum vitamin E/total lipids
 - d. Vitamin K: International Normalized Ratio (INR)
5. Presence of ascites
- Tertiary outcome measures:

All measurements will be made at 12 and 24 months of age:

 1. International Normalized Ratio (INR)
 2. Serum albumin concentration
 3. Pediatric End-Stage Liver Disease (PELD) score
 4. Platelet count
 5. Serum sodium concentration
 6. Serum bile acid concentrations
 7. Serum concentration of undercarboxylated prothrombin (PIVKA-II)
 8. Head circumference Z-score
 9. Mid-arm circumference and triceps skinfold thickness
 10. Health-related quality of life (HRQOL)
 11. Neurodevelopmental assessment (Bayley score)
 12. Immunologic response to routine childhood vaccination (at 18 months of age)

In addition, we will monitor study subjects for any potential adverse events that may result from the use of corticosteroids. Although no significant complications were reported in the uncontrolled clinical reports of corticosteroids as adjuvant treatment of biliary atresia⁴⁶⁻⁴⁹, we will be particularly cognizant of the need to carefully monitor the subjects to determine the safety of the proposed treatment.

4.F. Study Design and Intervention

4.F1. Administration of Study Drug or Placebo

Written informed consent will be obtained either after a decision is made by the attending physician at the ChiLDREN site that the infant will undergo an exploratory laparotomy with possible portoenterostomy, or within 72 hours after portoenterostomy. As part of the informed consent, parents/legal guardians will be informed of potential side effects of corticosteroids, as well as of potential adverse consequences of the sudden discontinuation of high doses of corticosteroids (after use for more than 2 weeks). Some of the potential side effects of corticosteroid medications are listed below. This information will be shared with the subject's parents at the time of enrollment and are included in the "ChiLDREN corticosteroid information sheet", which will also be given to the subject's parents. The strategy to carefully monitor for the side effects is outlined in the Section 7.D.

- Hypertension
- Hyperglycemia
- Increased appetite, fluid retention, and weight gain

- Increased crying and decreased sleeping
- Increased risk of infection
- Impaired linear growth
- Cataracts
- Decreased response to immunizations
- Gastrointestinal bleeding
- Pancreatitis
- Hypokalemia
- Impaired wound healing

Randomization will be performed by the DCC and either corticosteroid or placebo therapy will be initiated within 72 hours after portoenterostomy; doses will be adjusted according to the dosing schedule outlined in Table 4. The dose and regimen for corticosteroids were based on prior uncontrolled clinical reports in infants with biliary atresia⁴⁶⁻⁴⁹. The choice of the corticosteroid prednisolone is consistent with these reports, and may represent an additional safety feature in view of the lower plasma and biological tissue half-life that is typical for prednisolone when compared to dexamethasone. The decrease in half life of prednisolone may decrease the cumulative exposure to high levels of glucocorticoid function, thus decreasing the potential risk of toxicity to subjects randomized to receive corticosteroids. Corticosteroids or placebo will be given intravenously for at least 2 post-operative days or until the infant resumes oral or enteral feedings. When the infant is tolerating oral or enteral feedings, prednisolone or placebo will be given orally for the remainder of the course of study drug/placebo. Compounding of placebo by a registered pharmacist (see below) will match the corticosteroid product for appearance and taste.

Table 4. Schedule and Dosing of Corticosteroids or Placebo Following Portoenterostomy in Infants with Biliary Atresia.

Day/week of dosing	Corticosteroids*	Placebo
Days 1-7		
days 1-3	Methylprednisolone, IV – 4 mg/kg/day, divided BID	IV – Normal saline (same volume, BID)
days 4-7	Prednisolone, PO – 4 mg/kg/day, divided BID	PO – Placebo (same volume, BID)
Week 2	4 mg/kg/day, divided BID	PO same volume BID
Week 3	2 mg/kg/day, divided BID	PO same volume BID
Week 4	2 mg/kg/day, divided BID	PO same volume BID
Week 5	1 mg/kg/day, once a day	PO once a day
Week 6	1 mg/kg/day, once a day	PO once a day
Week 7	0.8 mg/kg/day, once a day	PO once a day
Week 8	0.6 mg/kg/day, once a day	PO once a day
Week 9	0.4 mg/kg/day, once a day	PO once a day
Week 10	0.2 mg/kg/day, once a day	PO once a day
Week 11	0.1 mg/kg/day, once a day	PO once a day
Week 12-13	0.1 mg/kg/every other day	PO every other day
Week 14	Stop	Stop

*Initial dosage will be based on subject’s weight. Subsequent doses will be adjusted based on subject’s weight measured monthly at each scheduled outpatient visit.

Infants who have received the live attenuated rotavirus vaccine (e.g. Rotateq) within 5 days prior to proposed administration of study drug are excluded from the study. Infants who have received the vaccine prior to this interval should not receive their first dose of steroids until a total of 5 days post vaccination has elapsed.

4.F2. Dose Reduction

In the event that a subject has a potential expected or unanticipated side effect of the study drug/placebo (such as irritability) but there is no indication to stop the study drug/placebo, the clinical site PI will have the option to reduce the dose of the study drug/placebo by 50%. The subject will then be monitored for improvement in these symptoms. If the symptoms improve within 48 hours, the subject will be maintained at the reduced dose for the remainder of the days planned for the original dose, as well as for the duration of treatment with this dose according to the normal taper schedule (Table 4). If symptoms do not improve/resolve, a further reduction by 50% of the new dose will be considered by the clinical site PI. Any reduction in the dosage of study drug/placebo will be reported to the DCC by the clinical site PI, along with the notification of the adverse event. If the symptoms persist beyond 48 hours and the clinical site PI judges it necessary that the study drug/placebo be discontinued, the tapering and discontinuation protocol outlined below will be followed.

4.F3. Tapering and Discontinuation of Study Drug or Placebo in the Event of a Serious Adverse Event (SAE) or Early Withdrawal

Blinded taper: If a SAE (see definition in Section 7.B3) is documented and thought by the clinical site PI to be possibly related to the study drug/placebo or if the subject withdraws from the study before the completion of the study drug/placebo, the clinical site PI will initiate a blinded taper of the study drug/placebo following the schedule outlined in Table 5 (below). The taper will be implemented in a blinded fashion in order to maintain objectivity in subject care and data collection during follow-up visits for the duration of the study.

Table 5. Tapering Protocol for Discontinuation of Study Drug or Placebo

Duration of treatment	Plan
Week 1	No need to taper; discontinue study drug or placebo
Weeks 2-8	Decrease dose to 0.6 mg/kg/day study drug/placebo orally x 7 days Then decrease the dose by 50% x 7 days and stop
Weeks 9-10	Decrease the dose by 50% for 7 days and stop
Weeks 11-13	Stop without taper

Unblinded taper: In the event of a life-threatening complication and when the physician treating the subject determines that knowing whether the subject was taking corticosteroid is essential to implement his/her treatment plan (e.g., need for stress dose of steroid in the setting of bacteremia and hypotension or invasive tissue sepsis with systemic symptoms), the study code will be broken to reveal if the subject was receiving placebo or corticosteroids. [The Safety Monitor and the DCC will be informed immediately by the filing of a SAE report.] In this setting, if the subject had been receiving corticosteroids, the tapering protocol will use a stress dose of hydrocortisone (50-62.5 mg/m²/24h) for 2-3 days, then physiologic replacement (20-25 mg/m²/24h) for 7 days, then half of the replacement dose for 7 days; the use of hydrocortisone instead of prednisolone or methylprednisolone in the setting of infection will minimize additional immunosuppression that would result from the glucocorticoid action of prednisolone during the taper schedule. Alternatively, replacement doses may be in the form of prednisolone (using the doses outlined for weeks 2-8 of Table 5) if the subject tolerates oral/enteral feedings.

4.G. Other Perioperative and Medical Management

All subjects with biliary atresia will undergo standard surgical portoenterostomy following the technical guidelines agreed upon by the ChiLDREN Surgical Committee (see Appendix). Postoperatively, subjects will receive intravenous medication to suppress gastric acid production (H₂ blocker or proton pump inhibitor, according to the local standard of care) until they resume oral/enteric feedings. Once they resume oral/enteric feedings, they will receive 12.5 mg BID oral ranitidine (2-6 mg/kg/day, see Section 4.M.7) during administration of study drug/placebo; ranitidine is approved by the FDA for use in children (1 month-16 years of age).

